## PROTOCOL SUMMARY

Protocol title	Prepivotal evaluation of the safety and effectiveness of the Omnipod Horizon™ Automated Glucose Control System in patients with type 1 diabetes
Protocol ID	G190267
Purpose	To evaluate the safety and effectiveness of the Omnipod Horizon™ Automated Glucose Control System in patients with type 1 diabetes.
Design	This study is a single-arm, multi-center, prospective clinical study
Enrollment	
Up to 48 subjects will be enrolled in the study in order to obtain a minimum of 36 evaluable subjects. The study will consist of two phases:
 
 
1) 14-day standard therapy phase, followed by;
 
2) 14-day hybrid closed-loop phase
 
 
Subjects will be enrolled across 6-8 clinical study sites. The 36 evaluable subjects will be comprised of two age cohorts as follows:
 
 
• 18 subjects aged 6-13.9 years
 
• 18 subjects aged 14-70 years
 

Indication	
The Omnipod Horizon™ Automated Glucose Control System is a single hormone insulin delivery system intended for the management of diabetes in persons requiring insulin. Continuous subcutaneous insulin infusion may be delivered by user-defined settings (manual mode) or automatically adjusted in response to feedback from a continuous glucose monitor (CGM).
 
The Omnipod Horizon™ System can automatically increase insulin delivery based on CGM sensor glucose values and can decrease or suspend delivery of insulin when the glucose value falls below or is predicted to fall below predefined threshold values. The Omnipod HORIZON™ System is interoperable with compatible iCGMs and ACE pumps.
 
The Omnipod Horizon™ System is designed to assist patients with diabetes in achieving glycemic targets set by their health care providers.

Study duration	The study is expected to be completed within 6-months which includes clinical site initiation to completion of all data entry and monitoring procedures.
Investigational devices	
The Omnipod Horizon™ Automated Glucose Control System is comprised of the following components:
 
 
• Omnipod Horizon™ tubeless, insulin delivery alternate controller enabled (ACE) pump (Pod) with the Horizon™ algorithm
 
• Omnipod Horizon™ Personal Diabetes Manager (PDM) which is a Samsung J3 locked down Android device that operates the Omnipod Horizon™ App.
 

Non-investigational, commercially available devices	
 
• Dexcom G6 - Continuous Glucose Monitoring (CGM) system
 
• Contour® Next One blood glucose meter (Ascensia Diabetes Care, [name])
 
• Precision Xtra ketone meter (Abbott Diabetes Care Inc., [name])
 

Safety objective	To evaluate the safety of the Omnipod Horizon™ Automated Glucose Control System in patients with type 1 diabetes
Primary safety endpoint	Proportion of subjects with serious device-related adverse events
Secondary safety endpoints	
 
Proportion of subjects with severe hypoglycemia during hybrid closed-loop
 
Proportion of subjects with diabetic ketoacidosis (DKA) during hybrid closed-loop
 

Primary effectiveness objective	To evaluate the effectiveness of the Omnipod Horizon™ Automated Glucose Control System
Primary effectiveness endpoints	
Percentage of time in range (70-180 mg/dL) during hybrid closed-loop compared to standard therapy for:
 
 
Target blood glucose (BG) challenge days (approximately hybrid closed-loop days 1-9)
 
Non-challenge days (approximately hybrid closed-loop days 10-14)
 
Overall (hybrid closed-loop days 1-14)
 

Secondary effectiveness objective	To evaluate additional glycemic measures of effectiveness of the Omnipod Horizon™ Automated Glucose Control System
Secondary effectiveness endpoints	
The secondary objective will be evaluated using the following per subject endpoints:
 
 
Glucose metrics from system CGM during the hybrid closed-loop phase will be compared to the standard therapy phase during the day, overnight, and overall: 
 
Mean glucose
 
% of time in range 70-180 mg/dL
 
% of time in range 70-140 mg/dL
 
% of time > 180 mg/dL
 
% of time <math>\geq</math> 250 mg/dL
 
% of time <math>\geq</math> 300 mg/dL
 
% of time < 70 mg/dL
 
% of time < 54 mg/dL
 
Standard deviation
 
Coefficient of variation
 
 
 
Glucose management indicator (GMI) based on overall mean glucose
 
Percentage of time in hybrid closed-loop as proportion of overall device usage time
 
Insulin requirements during the hybrid closed-loop phase will be compared to the standard therapy phase: 
 
Total daily insulin (TDI) (units, units/kg)
 
Total daily basal insulin (units, units/kg)
 
Total daily bolus insulin (units, units/kg)
 
 
 

Eligibility criteria	
Inclusion Criteria
 
Subjects must meet all of the following criteria to be included in the study:
 
 
1. Age at time of consent/assent 6-70 years
 
2. Subjects aged < 18 years must be living with parent/legal guardian
 
3. Diagnosed with type 1 diabetes for at least 6 months. Diagnosis is based on investigator's clinical judgment.
 
4. Deemed appropriate for pump therapy per investigator's assessment taking into account previous history of severe hypoglycemic and hyperglycemic events, and other comorbidities
 
5. Investigator has confidence that the subject can successfully operate all study devices and is capable of adhering to the protocol
 
6. Willing to use only the following types of insulin during the study: Humalog, Novolog, Admelog, or Apidra during the study
 
7. Must be willing to set target glucose between 130-150 mg/dL each for approximately 72-hours on predefined days during the hybrid closed-loop phase
 
8. Must be willing to extend their participation into the pivotal study if they continue to meet the protocol criteria
 
9. Willing to wear the system continuously throughout the study
 
10. A1C <10% at screening visit
 
11. Must be willing to use the Dexcom App on the Omnipod Horizon™ PDM as the sole source of Dexcom data (with the exception of the Dexcom Follow App) during the hybrid closed-loop phase
 
12. Subjects scoring ≥ 4 on the Clarke Questionnaire must agree to have an overnight companion, defined as someone who resides in the same home or building as the study subject and who can be available overnight
 
13. Able to read and speak English fluently
 
14. Subject must be in an AT&T covered area
 
15. Willing and able to sign the Informed Consent Form (ICF) and/or has a parent/guardian willing and able to sign the ICF. Assent will be obtained from pediatric and adolescent subjects aged < 18 years per State requirements.
 
 
Exclusion Criteria
 
Subjects who meet any of the following criteria will be excluded from the study:
 
 
1. A medical condition, which in the opinion of the investigator, would put the subject at an unacceptable safety risk
 
2. History of severe hypoglycemia (as defined in Section 11.3.3) in the past 6 months
 
3. History of DKA (as defined in Section 11.3.4) in the past 6 months, unrelated to an intercurrent illness, infusion set failure or initial diagnosis
 
4. Diagnosed with sickle cell disease
 
5. Diagnosed with hemophilia or any other bleeding disorders
 
6. Plans to receive blood transfusion over the course of the study
 
7. Currently diagnosed with anorexia nervosa or bulimia
 
8. Acute or chronic kidney disease (e.g. estimated GFR < 45) or currently on hemodialysis
 
9. History of adrenal insufficiency
 
10. Has taken oral or injectable steroids within the past 8 weeks or plans to take oral or injectable steroids during the course of the study
 
11. Unable to tolerate adhesive tape or has any unresolved skin condition in the area of sensor or pump placement
 
12. Plans to use insulin other than U-100 insulin intended for use in the study device during the course of the study
 

----------------------	---

	
13. Use of non-insulin anti-diabetic medication other than metformin (e.g. GLP1 agonist, SGLT2 inhibitor, DPP-4 inhibitor, pramlintide)
 
14. Current or known history of coronary artery disease that is not stable with medical management, including unstable angina, or angina that prevents moderate exercise despite medical management, or a history of myocardial infarction, percutaneous coronary intervention, or coronary artery bypass grafting within the previous 12 months.
 
15. For subjects >50 years old or with diabetes duration >20 years, abnormal electrocardiogram consistent with increased risk of arrhythmia, ischemia, or prolonged QTc interval (> 450 ms)
 
16. Thyroid Stimulating Hormone (TSH) is outside of normal range with clinical signs of hypothyroidism or hyperthyroidism
 
17. Pregnant or lactating, or is a woman of childbearing potential and not on acceptable form of birth control (acceptable includes abstinence, condoms, oral/injectable contraceptives, IUD or implant)
 
18. Participation in another clinical study using an investigational drug or device within the preceding 30-days or intends to participate during the study period
 
19. Unable to follow clinical protocol for the duration of the study or is otherwise deemed unacceptable to participate in the study per the investigator's clinical judgment.

Study schedule overview	
The study schedule consists of the following two phases:
 
 
1) 14-day outpatient standard therapy phase followed by;
 
2) 14-day hybrid closed-loop phase
 
 
Following subject screening, enrollment, and device training, subjects will commence the outpatient standard therapy phase of the study.
 
Current Dexcom G6 CGM users may provide data from a 14-day period within the last 30-days. The CGM data meeting the minimum criteria must be the most recent data from the last 30-days. For non-G6 users, subjects will wear a study CGM, in blinded mode, to record glucose measurements over 14-days while subjects manage their diabetes at home per their usual routine and remaining on their current MDI or pump therapy, and sensor, if applicable, for 14-days.
 
After completion of the standard therapy phase, subjects will be trained on the system and transition to the hybrid closed-loop phase initiating treatment with the Omnipod Horizon™ System. For the hybrid closed-loop phase, subjects will be divided into two groups:
 
Group 1:
 
 
1. N=16 subjects aged 6-70 years will participate in the hybrid closed-loop phase for the first 2-days while in a supervised hotel/rental house environment and then transition to 12-day outpatient environment 
 
o N=8 subjects aged 6-13.9 years
 
o N=8 subjects aged 14-70 years
 
 
 
 
Group 2:
 
 
2. N=20 subjects aged 6-70 years will participate in the hybrid closed-loop phase in a 14-day outpatient environment 
 
o N=10 subjects aged 6-13.9 years
 
o N=10 subjects aged 14-70 years
 
 
 

	
The first group of subjects (n=16) will commence the hybrid closed-loop phase in the hotel setting. On study day-3, subjects will transition to the outpatient setting for the remaining 12-days. After all subjects from the first group have completed the 2-day hotel phase, the second group of subjects may commence hybrid closed-loop. The second group of subjects (n=20) will use hybrid closed-loop in the outpatient setting for 14-days.
 
All subjects will participate in target glucose challenges during the hybrid closed-loop phase. In total, all subjects will complete 14-days of hybrid closed-loop control, with approximately 72-hours spent at target blood glucose levels set to 130mg/dL, 140mg/dL and 150mg/dL, respectively.
 
Clinical site staff will receive alerts through a remote monitoring system during the study.
 
After each subject in the prepivotal study has successfully completed 14-days of hybrid-closed loop, they may immediately transition to and enroll in the pivotal study bypassing standard therapy (Phase 1) and continuing with the pivotal hybrid closed-loop phase (Phase 2). Remote monitoring will be discontinued as each subject enrolls in the pivotal study.
 
After 16-subjects from the prepivotal study have completed a minimum of 10-days of hybrid-closed-loop, the Data Safety Monitoring Board (DSMB) will convene and if the system is determined to be safe, the pivotal study may open enrollment to additional subjects for the hybrid closed-loop phase (Phase 2).
 
The standard therapy phase (Phase 1) of the pivotal study may commence in parallel to the prepivotal study.

--	---

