### 2.1 Device Description of the Omnipod Horizon™ System

The Omnipod Horizon™ System intended for commercialization is composed of three primary components as shown in Figure 1.

- Omnipod Horizon™ Controller – Horizon App (PDM) and Algorithm
- Omnipod Horizon™ ACE Pump – Pod
- iCGM – Dexcom G6

The Omnipod Horizon™ System will provide automated insulin delivery when connected to CGM. The system is expected to reduce hypoglycemia without incurring an unacceptable increase in hyperglycemia and mean glucose. The system is also expected to reduce the extent and magnitude of hyperglycemia associated with meals. Optimal post-prandial control requires the user to deliver meal boluses as in current open-loop therapy, but the normal operation of the control algorithm will be expected to

compensate for mismatched meal boluses and prevent prolonged hyperglycemia. The system uses a control-to-target strategy that attempts to achieve and maintain a set target glucose level.

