### Automated Mode

In Automated Mode, the system will support the use of multiple target glucose values, currently intended to be 110-150 mg/dL at commercialization, in 10 mg/dL increments. The experience for the user will reflect current setup flows whereby the health care provider assists the user to program basal rates, glucose targets and bolus calculator settings. These in turn will inform the MPC algorithm for insulin dosing parameters. The insulin dosing parameters will be adapted over time based on the total daily insulin (TDI) delivered during each Pod use. A temporary hypoglycemia protection mode (Hypo Protect) may be implemented by the user for various time durations during Automated Mode. With Hypo Protect, the algorithm reduces insulin delivery and is intended for use over temporary durations when insulin sensitivity is expected to be higher, such as during exercise.

The Omnipod Horizon™ System will include two apps on a locked-down smartphone (the Samsung J3), referred to as Personal Diabetes Manager (PDM): the Horizon App and the Dexcom App. The Horizon App, which will have a similar interface to the cleared Omnipod® DASH System (K191679), will allow the use of large text, graphics, and on-screen instructions to prompt the user through set-up processes. It will also be used to program the user's custom basal insulin delivery profile, check the Pod status, initiate bolus doses of insulin, make changes to a patient's insulin delivery profile, handle system alerts and alarms, and enter Automated Mode.

The Dexcom App interface is identical to the current app of the interoperable Dexcom G6 Continuous Glucose Monitoring System (K191450) and will provide CGM data, alerts, and alarms to the user.

The Horizon App and Dexcom App will not directly communicate with one another. Instead, the iCGM transmitter will communicate EGV (estimated glucose values) directly to the Pod. The Dexcom transmitter number must be entered into the Horizon App, and this information is sent to the Pod to allow transmission of EGV. The Pod will pair directly to the transmitter to receive EGV for the algorithm and also sends the EGV back to the Horizon App as shown in Figure 1.

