### **2.4 TARGET BLOOD GLUCOSE CHALLENGES**

All subjects take part in the prescribed target blood glucose (BG) challenges for approximately 72 consecutive hours each:

- Target BG of 130 mg/dL during HCL days 1-3
- Target BG of 140 mg/dL during HCL days 4-6
- Target BG of 150 mg/dL during HCL days 7-9
- Target BG of subject's choosing of 110-150 mg/DL during HCL days 10-14

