### 4.2 PRIMARY ANALYSIS

There are no pre-specified hypotheses associated with the primary effectiveness endpoints. Summary statistics will be presented by age cohort for all endpoints, stratified by time points of interest (e.g., day, night, overall). The primary effectiveness endpoints will be summarized for modified Intention to Treat (mITT) and Per Protocol (PP) analysis sets, where the percentage of TIR during ST phase will be compared to the percentage of TIR during HCL BG challenge days, HCL non-challenge days, and over the entire HCL.

Since the target BG challenges require a specific setpoint, the start of the challenge will be the first record at the given setpoint, and the end of the challenge will be last record at the same setpoint.

All statistical comparisons will be conducted at a two-sided significance level of 5% using a paired t-test. If the assumptions for parametric test are grossly violated, a non-parametric method such as Wilcoxon signed rank test may be used. Since the results of endpoint analyses will not be used to support clinical claims, no adjustment for multiplicity will be performed.

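### The planned tables average over glucose targets: no result, and no exposure, is prespecified by setpoint

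*Protocol*

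**What the plan says.** **Targets.** SAP 2.4 sets "Target BG of 130 mg/dL during HCL days 1-3", "Target BG of 140 mg/dL during HCL days 4-6" and 150 mg/dL on days 7-9, about 72 hours each, followed by "Target BG of subject's choosing of 110-150 mg/DL during HCL days 10-14". Protocol 9.1 and Table 4 agree. Protocol 9.6 has sites check at Visits 7 to 9 that at least 72 hours of data exist at each designated level.

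**Device.** Protocol 2.1 states: "The system uses a control-to-target strategy that attempts to achieve and maintain a set target glucose level". The Automated Mode section describes "multiple target glucose values, currently intended to be 110-150 mg/dL at commercialization", in steps of 10 mg/dL, so five targets are available.

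**Primary endpoint.** Time in range is compared with standard therapy over three windows: "Target blood glucose (BG) challenge days (approximately hybrid closed-loop days 1-9"; "Non-challenge days (approximately hybrid closed-loop days 10-14"; and all 14 days. SAP 4.2 plans these three comparisons and no others. It dates a challenge by setpoint ("the start of the challenge will be the first record at the given setpoint"), with the end at the last record at that setpoint.

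**Secondary range endpoints.** SAP 6.1 sends these, including time below 70 and below 54 mg/dL, through the primary analysis.

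**Strata.** SAP 4.3 and 6.5 name phase, age cohort and day or night. Protocol 12.4 adds Dexcom G6 use at screening. Setpoint is not named. SAP 4.3 and 6.5 allow other subgroups but commit to none.

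**The concern.** The target is the setting that a control-to-target device acts on, and the study goes to the trouble of imposing three values of it in turn. Averaging over them leaves a challenge figure that describes no target anyone would use. It also leaves a non-challenge figure that depends on which targets subjects happened to choose, a mix that the SAP does not plan to report.

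Two things are at stake. First, a reader of the planned tables could not tell whether time in range, or time below 70 mg/dL, moved across 130, 140 and 150 or stayed level. Second, a non-challenge result labelled 110-150 mg/dL might contain much, little or no time at 110-120 mg/dL. Those two values are never imposed, no minimum exposure to them is set, and the tables would not reveal how much occurred.

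**Working it through.** **Is there a plan figure to reproduce?** No. The sample size is stated not to be hypothesis-driven (Protocol 12.2, SAP 4.1), and no effect size, SD or power is given. The structure does add up: 3 + 3 + 3 + 5 = 14 closed-loop days; 18 + 18 = 36 and 16 + 20 = 36 subjects.

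**Step 1. Data per target.** SAP 6.2 says records come about every 5 minutes, which is 24 × 60 / 5 = 288 per day. With complete data, per subject:

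| Window | Days | Records | Share of 14 days |
|---|---|---|---|
| Each imposed target | 3 | 864 | 21.4% |
| Challenge window | 9 | 2,592 | 64.3% |
| Free-choice window | 5 | 1,440 | 35.7% |
| Overall | 14 | 4,032 | 100% |

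**Step 2. What pooling removes.** Time in range is in-range records divided by evaluable records (SAP 7.4). With equal records per block, the challenge figure is (p130 + p140 + p150) / 3. Assumed values, for illustration only:

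- Time in range 70/70/70, 76/70/64 and 80/70/60: each gives 70.0.
- Time below 70 mg/dL of 1.5/1.5/1.5 and 2.5/1.5/0.5: each gives 1.5.

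The pooled number is the same for a flat response and for a steep one.

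**Step 3. The free-choice window.** Here the figure is the sum over k of w_k × p_k, where w_k is the share of records at target k (110, 120, 130, 140 or 150). The weights are set by the subject and are not planned for reporting. The combined weight at 110 and 120 can be anything from 0 to 1, which is 0 to 5 × 24 = 120 hours per subject. Over 36 subjects that is 0 to 4,320 of 36 × 14 × 24 = 12,096 subject-hours.

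**Step 4. Is a by-setpoint result worth printing?** The 95% half-width for a within-subject difference such as 150 versus 130 is t(0.975, n-1) × SD / √n. The SD of the difference is not in the documents, so a range is assumed:

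| Assumed SD (points) | n = 36 | n = 18 (one cohort) |
|---|---|---|
| 6 | 2.0 | 3.0 |
| 10 | 3.4 | 5.0 |
| 14 | 4.7 | 7.0 |

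For example, with SD 10 and n = 36: 2.030 × 10 / 6 = 3.4. Precision is adequate for description. These intervals cover sampling error only and say nothing about confounding with time.

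**The case against.** **The study can show this.** A reader might infer that the design is incapable of showing how control varies with target. The documents do not support that. About 72 hours are scheduled and checked at each imposed target, the data portal reports time at each target (Protocol 3), SAP 4.2 already cuts records by setpoint, and SAP 4.3 permits further subgroups. This objection stands: the gap is in the prespecified analysis, not in the data.

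**The challenges serve another purpose.** Protocol 1 gives their aim as exposure to stressors. There are no hypotheses (SAP 4.2) and no success criteria (SAP 2.5), and results support no clinical claims. A pooled split fits that aim, and sponsor reviews of controller data are planned separately (SAP 7.8). This rules out a formal target-response test, but it is no reason to omit a descriptive result at each stressor.

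**A by-setpoint contrast is confounded.** This stands in full. Every subject goes through 130, then 140, then 150. Target therefore moves with day of use and with adaptation of insulin dosing across Pods (Protocol, Automated Mode). For Group 1 (16 of 36), two supervised hotel days with encouraged exercise (Protocol 9.2) fall in the 130 block. A flat table would not show that the device ignores its target, because adaptation could offset a gradient.

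**Targets of 110-120 mg/dL are self-selected.** Subjects who choose them may differ from those who choose 150, so a comparison there is selected and largely between subjects. What remains is the need to report exposure.

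**The size of the loss cannot be modelled from the documents.** Setting mean glucose at target plus a constant would produce a gradient, but it assumes the perfect tracking that is in question.

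**Conclusion.** The concern holds as a limit of the planned tables. No result by setpoint is prespecified for time in range or for time below 70 or 54 mg/dL, and no table reports exposure at each target. The pooled challenge figure gives each imposed target a weight of one third when data are complete. The pooled non-challenge figure rests on an unreported mix in which 110-120 mg/dL may account for none or all of the nominal 120 hours per subject.

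The size of any real gradient is unknown. The values in Step 2 and the SDs in Step 4 are assumptions, used to show that masking is possible and that a descriptive contrast is feasible.

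A reader might also infer that the missing table weakens the safety review that may open pivotal closed-loop enrollment. The documents do not support that. The review follows 16 subjects with at least 10 closed-loop days (Protocol 11.8), when the free-choice period has barely begun, and no SAP table is tied to it.

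The pooled endpoints remain valid for what they claim. This is a cheap improvement worth making, not a fault in the primary comparison, and it implies no view on which target should be used.

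**What to change.** Keep the pooled endpoints. Because the SAP prevails over the protocol (SAP 1), make the change in SAP 4.2 and 6.1, with a cross-reference in 6.3 for mean glucose:

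- Add a descriptive table by setpoint giving time in range, mean glucose, time below 70 and below 54 mg/dL, hours, and number of subjects, by age cohort and overall.
- Keep the imposed blocks (130, 140, 150) separate from the free-choice rows (110 to 150), eight rows in all. State that an imposed block ends when the next scheduled period begins. A subject may choose 130, 140 or 150 again on days 10-14, and the rule of the last record at the same setpoint could then run past the block.
- For 130/140/150, give within-subject differences with 95% intervals.
- State above the table that the results are descriptive and not causal, naming the fixed ascending order, insulin adaptation, Group 1's hotel days within the 130 block, and self-selection on days 10-14.

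Cost: SAP wording and one extra table from data already recorded with the setpoint. There are no new visits, subjects or changes to conduct. Some chosen targets may have few subjects, and those rows will be sparse.
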